9.1.9. Cardiovascular Events

For any AEs and SAEs that are classified as one of the following Cardiovascular Events, additional information will be collected on the eCRF:

- Arrhythmias
- Congestive heart failure
- Cerebrovascular events/stroke and transient ischemic attack
- Deep venous thrombosis/pulmonary embolism
- Myocardial infarction/unstable angina
- Peripheral arterial thromboembolism
- Pulmonary hypertension
- Coronary revascularization
- Peripheral revascularization
- Valvulopathy

All data collected on the eCRF pages will be listed. A listing presenting subjects with a least one cardiovascular event during the study will also be displayed.

9.2. Clinical Laboratory Evaluations

Clinical laboratory safety test (hematology, serum chemistry, fasting lipids and other tests) will be collected as specified in [Appendix 13.1](#) and will be analyzed by a central laboratory.

All summaries will be based on the standard international units.

Laboratory data will be listed and abnormal values will be flagged in the data listings. A listing of laboratory data outside of normal ranges will be presented by actual treatment group. A listing of laboratory test reference ranges will also be provided. Test reference ranges used will be the references range provided with the lab results.

Summary tables presenting observed values and changes from Baseline will be presented for clinical laboratory tests with numeric values by actual treatment group for subjects in the Safety set, separately for each laboratory category.

The assessment of laboratory toxicities will examine all Common Terminology Criteria for Adverse Events (CTCAE V4.03) gradable laboratory tests. The National Cancer Institute Common Terminology Criteria for Adverse Events (NCICTCAE) will be used to grade laboratory gradable abnormalities. Maximum CTCAE post-Baseline grade will be summarized over time for each CTCAE gradable laboratory parameter. Summary of CTCAE grade shifts from Baseline will also be produced over Time and for the worst post-baseline value. CTCAE grades will be displayed in laboratory listings.

Abnormal (i.e. outside of laboratory test reference ranges) chemistry and hematology values will be summarized by actual treatment. Shift from baseline tables of normal ranges by actual treatment will also be provided for the chemistry and hematology parameters, over time and for the worst-post baseline value.

A summary table for abnormal laboratory tests Alanine Aminotransferase (ALT), Aspartate aminotransferase (AST), Absolute Neutrophil Counts and Platelet Counts will be generated over time and the following abnormal categories will be used:

Table 6 Abnormal Categories for AST, ALT, Neutrophils and Platelet Counts

Test Name	Categories		
AST	≥3 x ULN	≥5 x ULN	
ALT	≥3 x ULN	≥5 x ULN	≥8 x ULN
Neutrophils	<0.5 x 10 ⁹ /L	0.5 to ≤1.0 x 10 ⁹ /L	>1.0 x 10 ⁹ /L
Platelet Counts	<50 x 10 ⁹ /L	50 to ≤ 100 x 10 ⁹ /L	>100 x 10 ⁹ /L

ULN: upper limit of normal

Plots of laboratory parameters over time will be provided. A scatter plot of maximum vs. Baseline ALT will be produced. A scatter plot of maximum ALT vs maximum Total Bilirubin will be produced.

Individual plot over time of aspartate aminotransferase, alanine aminotransferase, alkaline phosphatase and total bilirubin will be created, only for subjects with a total bilirubin > 2 ULN and alanine aminotransferase > 3 ULN at the same visit.

9.2.1. Hematology and Fasting Lipids

Hematology assessments presented in [Table 7](#) are taken at predefined visits as specified in [Appendix 13.1](#) (i.e. at Screening, Week 0, Week 2, Week 4, Week 8, Week 12, Week 16, Week 20, Week 24, Week 28, Week 32, Week 36, Week 40, Week 44, Week 48 and Week 52) including unscheduled visits used to assess flares and early withdrawal visits. Fasting lipids as presented in [Table 7](#) will be summarized as part of the hematology assessment. Fasting lipids are collected at Week 0, Week 12, Week 24, Week 36, and Week 52.

Table 7 Hematology and Fasting Lipids Parameters

Hematology		
Hemoglobin	Hematocrit	Red blood cell (RBC) count
White blood cell (WBC) count with differential	Neutrophils, absolute	Neutrophils, segs (%)
Neutrophils, bands (%)	Basophils (%)	Eosinophils (%)
Eosinophils, absolute	Lymphocytes (%)	Monocytes (%)
Platelet count	Hemoglobin A1c	
Fasting lipids		
Total cholesterol	Low density lipoprotein (LDL)	High density lipoprotein (HDL)
Triglycerides	Total cholesterol to HDL ratio	

9.2.2. Serum Chemistry

Serum chemistry assessments presented in CPK and LDH will be listed as part of Chemistry parameters but will not be summarized.

Table 8 are taken at predefined visits as specified in [Appendix 13.1](#) (i.e. at Screening, Week 0, Week 2, Week 4, Week 8, Week 12, Week 16, Week 20, Week 24, Week 28, Week 32, Week 36, Week 40, Week 44, Week 48 and Week 52), including unscheduled visits used to assess flares and early withdrawal visits. CPK and LDH will be listed as part of Chemistry parameters but will not be summarized.

Table 8 Serum chemistry Parameters

Serum Chemistry		
Sodium	Potassium	Chloride
Bicarbonate	Blood urea nitrogen (BUN)	Creatinine
Glucose	Aspartate aminotransferase	Alanine aminotransferase
Alkaline phosphatase	Calcium	Phosphate
Albumin	Total protein	Bilirubin, direct, indirect and total

9.2.3. Other Laboratory Variables

To characterize changes in biomarkers of disease activity, absolute value and change from Baseline in ESR and CRP will be summarized over time.

Serology for virus infection (serology for human immunodeficiency virus (HIV), hepatitis B surface antigen, hepatitis B core antibody, and hepatitis C antibody) will be performed at Screening. All results (except serology for HIV) will be listed.

All QuantiFERON-TB Gold test results will be listed.

Serum pregnancy test will be performed at Screening, for premenopausal women only. Urine test will be conducted following the Screening visit, as specified in [Appendix 13.1](#) (i.e. at Screening, Week 0, Week 4, Week 8, Week 12, Week 16, Week 20, Week 24, Week 28, Week 32, Week 36, Week 40, Week 44, Week 48 and Week 52). Pregnancy tests will be listed.

All available biomarkers will be listed (CTX-1, P1NP and IFN- γ are expected for a subset of subjects/visits).

Table 9 Other Laboratory Parameters

Other tests	
Serum and urine pregnancy test for premenopausal women only	
Serology for human immunodeficiency virus, hepatitis B surface antigen, hepatitis B core antibody and hepatitis C antibody	
C-reactive protein (CRP)	Erythrocyte sedimentation rate (ESR)
QuantiFERON-TB Gold	

9.3. Vital Sign Measurements

Vital signs assessments are taken as specified in [Appendix 13.1](#) (i.e. at Screening, Week 0, Week 2, Week 4, Week 8, Week 12, Week 16, Week 20, Week 24, Week 28, Week 32, Week 36, Week 40, Week 44, Week 48 and Week 52).

Summary table and change from baseline table will be presented for vital sign data, including systolic blood pressure (mmHg), diastolic blood pressure (mmHg), heart rate (beats/min), temperature ($^{\circ}$ C) and weight (kg), over time by actual treatment group. All vital sign data by subject will be presented in a listing. A summary of worst case emergent (i.e. post-baseline) vital sign results by normal range category will be created and displayed by actual treatment group.

Normal ranges for vital sign are displayed in the table below:

Vital Sign Parameter (Absolute)	Units	Normal Range Limit	
		Lower	Upper
Systolic Blood Pressure	mmHg	< 85	> 160
Diastolic Blood Pressure	mmHg	< 45	> 100
Heart Rate	Bpm	< 40	> 110
Temperature	°C		≥ 38.3

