#### **7.5.1.5. Other Adverse Events of Special Interest for Sirukumab**

##### **Laboratory parameter abnormalities**

IL-6 is a pleiotropic cytokine necessary for hematopoiesis and IL-6 inhibition has been shown to cause a reduction in both neutrophils and platelets. In addition, IL-6 inhibition has been associated with reversible elevation in liver enzymes. Mechanisms by which

this might occur include inhibition of the hepatoprotective effect of IL-6, leaving hepatocytes susceptible to effects of toxins and other stresses. Lipid abnormalities have also been observed, both in the sirukumab Phase 2 study C1377T04, as well as with other anti-IL-6 agents. The mechanism by which this occurs is not fully understood.

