4.5. Definition of Baseline Value and Study Day

Baseline for Part A is defined as the last non-missing evaluation, including screening, re-screening and unscheduled assessments, prior to first SC IP, unless otherwise specified.

For assessments prior to the first SC IP date, the study day will be calculated as:

$$\text{Assessment date} - \text{First SC IP date}$$

For assessments on or after the first SC IP date, the study day relative to the Part A first SC IP date (i.e. the number of days from first dose date) will be calculated as:

$$\text{Assessment date} - \text{First SC IP date} + 1 \text{ day}$$

If the assessment date is completely missing or partial, the study day will be missing.

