Only demographic and baseline characteristic as well as Safety will be displayed for Part B. All demographic and baseline characteristic as well as Safety summaries produced for Part A will be produced for Part B. Part B outputs will be displayed using the same general layout of Part A outputs, using the same Part A group as the treatment groups.

Each output will be split using a by-line which will contain information on Part B:

- “Never Received OL Sirukumab during Part B” will include all subjects who did not take a dose of Received OL Sirukumab during Part B.
- “Received at Least 1 Dose of OL Sirukumab during Part B” will include all subjects who took at least one dose of OL Sirukumab during Part B.

The Baseline for Part B will be the last measurement done up to and including the Week 52 visit date of Part A.

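### Emergent vital-sign counts ignore the baseline category, and the Week 52 baseline leaves Part B change and shift tables without a pre-sirukumab reference in Arms A–C

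*SAP*

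**What the plan says.** **Vital signs, SAP 9.3.** Three outputs are planned. The first is by visit: "Summary table and change from baseline table will be presented for vital sign data". The second is subject-level: "All vital sign data by subject will be presented in a listing". The third is the categorical table: "A summary of worst case emergent (i.e. post-baseline) vital sign results by normal range category will be created". The limits for that table are in the same section (for example systolic pressure below 85 or above 160 mmHg). The baseline category plays no part in it.

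**Laboratory data, SAP 9.2.** Here the baseline is used: "Shift from baseline tables of normal ranges by actual treatment will also be provided for the chemistry and hematology parameters". These shift tables are produced over time and for the worst post-baseline value, and CTCAE grade shifts are added.

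**Baselines.** SAP 4.5 gives a pre-drug reference for Part A: "Baseline for Part A is defined as the last non-missing evaluation, including screening, re-screening and unscheduled assessments, prior to first SC IP". SAP Section 11 (Part B) moves it: "The Baseline for Part B will be the last measurement done up to and including the Week 52 visit date of Part A". The same section carries the safety outputs over: "All demographic and baseline characteristic as well as Safety summaries produced for Part A will be produced for Part B". Part B outputs keep the Part A arms as columns and are split by whether any open-label sirukumab was taken.

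**The concern.** **Emergent vital signs.** The word normally means new or worse than before treatment. Elsewhere the SAP uses it that way: under SAP 9.1 a treatment-emergent adverse event has to start within the exposed period. Under 9.3, a subject with systolic pressure above 160 mmHg at baseline and again at Week 2 is counted as emergent high. Subjects are aged 50 or over and enter on 20–60 mg of prednisone, so some out-of-range baseline pressures are plausible, although the documents give no rate.

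**Part B baseline.** Protocol 7.5.1.5 expects laboratory effects of the drug class: "IL-6 inhibition has been shown to cause a reduction in both neutrophils and platelets". If Week 52 is on drug, a Part B change from Week 52 does not measure the sirukumab effect. It measures what happened after that effect was already present.

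Changes in vital signs, hematology and chemistry are named safety endpoints in Part A and serve the long-term safety objective in Part B, so these displays should be readable on their own.

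**Working it through.** The plan states no figure for this point, so there is nothing to reproduce. The check is of the definitions, with illustrations on assumed rates.

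**1. Emergent vital signs**

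Let b be the share out of range at baseline, and q the true new-onset rate among those in range. Neither is in the documents. Assume everyone out of range at baseline is out of range at least once later; if fewer are, the effect is smaller.

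Displayed emergent rate = b + (1 − b) × q.

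| b | q = 0 | q = 5% | q = 10% | Pre-existing share at q = 5% | Displayed ratio, 10% v 5% | Displayed difference, 10% v 5% |
|---|---|---|---|---|---|---|
| 5% | 5% | 9.75% | 14.5% | 51% | 1.49 | 4.75 points |
| 10% | 10% | 14.5% | 19.0% | 69% | 1.31 | 4.5 points |
| 20% | 20% | 24.0% | 28.0% | 83% | 1.17 | 4.0 points |

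Example for b = 10%: 0.10 + 0.90 × 0.05 = 0.145 and 0.10 + 0.90 × 0.10 = 0.19. The ratio is 0.19 / 0.145 = 1.31 and the pre-existing share is 0.10 / 0.145 = 69%.

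The true ratio is 2.0 and the true difference 5 points. The ratio is diluted heavily. The difference shrinks only by the factor 1 − b.

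With new-onset rates of 20% v 10% and b of 5%, 10% or 15%, the displayed ratios are 24.0/14.5 = 1.66, 28.0/19.0 = 1.47 and 32.0/23.5 = 1.36.

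Randomization balances b in expectation. At the planned sizes of 51 (Arm A) and 34 (Arm D), chance imbalance in b has SD = √[b(1 − b)(1/51 + 1/34)], which is 4.8, 6.6 and 8.9 points for b = 5%, 10% and 20%. That noise goes straight into the displayed contrast.

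**2. Status of Week 52 in Arms A–C**

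- Injections run every 2 weeks from Week 0, so the last blinded one before Week 52 falls at Week 50. Arm C alternates active and placebo starting with active, so its last active dose falls at Week 48.
- Protocol 6.8 allows at least 70 days (10 weeks) for sirukumab to become undetectable. Week 52 is 2 to 4 weeks after the last active dose.
- SAP 11.5 classes adverse events within 16 weeks of the last injection as exposed, even with no open-label drug. The plan thus treats the start of Part B as exposed time for adverse events and Week 52 as baseline for laboratory and vital-sign data.

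**3. Effect on the Part B change column**

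Let d be the on-drug shift at Week 52 and f the fraction still present at a Part B visit.

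- Change from Week 52 = −(1 − f) × d.
- Change from the pre-drug value = f × d.

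With an assumed d = +5:

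- f = 1 gives 0 from Week 52 and +5 from pre-drug.
- f = 0.5 gives −2.5 and +2.5.
- f = 0 gives −5 and 0.

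A laboratory example with invented values: neutrophils of 5.0 before drug, 1.4 at Week 52 and 1.3 on open-label drug. The Part B change is 1.3 − 1.4 = −0.1, against 1.3 − 5.0 = −3.7 from the pre-drug value.

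**The case against.** A reader might infer that lasting sirukumab effects vanish from the report, or that nothing in the SAP lets one recognise a pre-existing abnormality. The documents do not support either reading.

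- Part A change tables and laboratory shift tables use the pre-drug baseline. In the example above, the fall from 5.0 to 1.4 appears there.
- SAP Section 4 has baseline, visit value and change shown together, so the 1.3 is visible among the Part B observed values.
- Maximum post-baseline CTCAE grade, out-of-range summaries and the fixed ALT, AST, neutrophil and platelet categories do not depend on baseline and are repeated for Part B.
- The worst-case vital-sign table itself ignores baseline, so a persistent out-of-range value still shows in Part B.
- All data are listed.

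A reader might also take Week 52 as on drug for everyone in Arms A–C. It is not: subjects who stopped injections permanently could remain in the study and reach Week 52 off drug.

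Other fair points: the SAP states openly what it means by emergent; baseline exceedance is balanced in expectation; Part B columns keep the arms apart; every rate above is assumed; and these are descriptive tables in a terminated study.

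All of that stands and limits the size of the point. It does not remove it. By-visit means cannot say how many subjects changed category, and listings leave the reader to count. Part A tables end at Week 52 and Part B tables start there, so no planned summary gives change or shift from pre-drug into Part B.

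**Conclusion.** The point holds in a limited form. As written, SAP 9.3 counts pre-existing out-of-range vital signs as emergent, and no planned summary table separates them from new ones. Counts are inflated in all arms and ratios between arms are pulled towards 1. The size depends wholly on the baseline rate, which the documents do not give; for 5% to 20%, a true ratio of 2.0 (10% against 5%) would display as 1.49 to 1.17.

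The Week 52 baseline affects only the Part B change and shift displays, and only for Arms A–C subjects still on treatment at Week 52. There, persistent effects drop out and washout appears as change.

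Practical impact is limited. No test or decision rule rests on these tables. SAP 1.1 reports that few subjects completed Week 52, and Part B entry requires completing Part A, so Part B numbers must be small; the documents give no count. It is a cheap improvement in presentation, not a threat to the safety conclusions.

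**What to change.** **SAP 9.3.** Tabulate the worst post-baseline vital-sign category by baseline category, with a row for missing baseline. Label as emergent only a category worse than at baseline. This matches what SAP 9.2 already does for chemistry and hematology.

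**SAP 11.** Keep Week 52 as the Part B baseline. Beside it, for Arms A–C, add laboratory and vital-sign change and shift from the Part A pre-treatment baseline of SAP 4.5.

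**Arms D and E.** Leave Week 52 as it stands, since it is already free of sirukumab. Moving to the last value before the first open-label dose would gain little: protocol Table 3 schedules no hematology or chemistry after Part B Week 16 in subjects not on open-label drug, so that value could be old.

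**Cost.** SAP wording and a few more descriptive tables. No new data are needed.

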9.4. Signs and Symptoms of GCA

At Baseline and each subsequent week, a clinical assessment of GCA is performed.

A summary table will be provided over time for each scheduled visit, with the number of subjects with each of the signs and symptoms, when no flare and when flare.

Clinical assessment of GCA will be listed in detail.

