3.4. Dose Adjustment/Modifications

No dose adjustment of sirukumab will be allowed in this study.

4. General Statistical Considerations

All analyses detailed in this SAP will be conducted using Statistical Analysis System (SAS)[®] statistical analysis software version 9.3 or higher (SAS Institute, Inc., Cary, North Carolina, USA). All SAS programs used to generate analytical results will be developed and validated according to PPD SAS programming standards and validation procedures.

Summary data will be presented in tabular format by treatment. Continuous variables will be summarized by descriptive statistics including number of subjects (N), mean, standard deviation (SD), median, minimum, and maximum.

Mean and median will be displayed to 1 more decimal place than the measured value. The SD will be displayed to 2 more decimal places than the measured value. Minimum and maximum will be displayed to the same decimal place as the measured value.

Categorical data (such as sex) will be summarized by number and percentage of subjects in each category. Percentages will be suppressed when the count is zero. A row denoted “Missing” will be included in count tabulations where necessary to account for missing values. The denominator for all percentages will be the number of subjects within the treatment (randomized or actual) group for the analysis set of interest, unless otherwise specified. Percentages which differ from 100% will be presented to 1 decimal place and 100% will be presented without a decimal.

Change from Baseline is the post-baseline value minus the baseline value. If the baseline or post-baseline value is missing, then the change from baseline is set to missing. For each scheduled post-baseline time point where change from Baseline is evaluated for continuous variables, descriptive statistics will be displayed for the values at Baseline, values at the scheduled post-baseline time point, and values for change from Baseline at the scheduled post-baseline time point for the set of subjects who have data at both Baseline and the time point being assessed. Early withdrawal visits as well as 16-week follow-up visits are considered as scheduled visits.

In case of multiple assessments for a scheduled visit, the last non missing assessment for this visit will be used for the summaries over time. All results will be listed.

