4.4. Analysis Visits

Data will be presented and analyzed according to the visit recorded in the database. For other efficacy and safety data that visit are entered, no visit windows will be defined as sites should have case report form (eCRF) instructions and training to ensure reasonable data entry. If a visit happens outside the protocol-defined window (Week X \pm 3 days), one of the following will be occur:

- If it is recorded as Week X visit, no visit re-mapping will be done (except for PRO endpoints and Part B visits) and the recorded visit will be used in all analysis.
- If it is recorded as unscheduled visit, it will be treated as unscheduled visit.

In general, only those assessments which are assigned to an analysis visit will be included in the summary tables and figures and will be presented by visit. Unscheduled visits will not be included in summary tables or figures, with the following exceptions: if the table or figure includes data values for all post-baseline assessments (worst/best/maximum/minimum post-baseline assessments), or for tables which report the values during a period of time, unscheduled visits will be included. All unscheduled visits will be included in the listings.

When reporting results or events that are reported on an ongoing basis, such as cumulative prednisone dose or flare at Week X: All results/events will be taken into account that occur inclusively between the day after the Week X-1 visit and the day of the Week X visit. The actual day of the Week X visit will always be taken into account as the day of visit X, even if the actual visit occurred outside of planned visit window.

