4.6.2. Sustained Remission

4.6.2.1. Main Analysis

The following procedures will be used to handle missing data for derivation of sustained remission (i.e. endpoints mentioned in [Section 8.1](#) and [Section 8.2.2](#)):

1. Any subject who is classified as a treatment failure (as per definition of [Section 4.6.1](#)) will be considered as not achieving sustained remission for the primary efficacy analysis and the supportive analyses of the primary efficacy endpoint.

2. Subjects with all four of the components of the primary endpoint missing at two consecutive scheduled visits will be considered as not achieving sustained remission for these two visits.
3. Subjects with all the components missing at Week X ($X \neq 52$) visit will be considered as achieving sustained remission at Week X visit if achieving sustained remission at the neighboring visits; as not achieving sustained remission otherwise. Data recorded at unscheduled visits will be taken into account based on the unscheduled visit date and will be associated with the next scheduled visit occurring after the unscheduled visit date.
4. Subjects with at least one of the four components of the primary endpoint missing at Week 52 visit will be considered as not achieving sustained remission at Week 52 visit.
5. When only a subset of the components is missing at Week X visit, the rules will be applied to the components first and then the imputed components are used to impute the values at post-baseline values. Similar rules as for complete missing visits are applied:
 - a. Subjects with some components missing at 2 consecutive visits will be considered as not achieving sustained remission for the missing components at these 2 visits.
 - b. Subjects with some components missing at Week X ($X \neq 52$) visit will be considered as achieving sustained remission for the missing components at Week X visit if achieving sustained remission at the neighboring visits; as not achieving sustained remission otherwise
 - c. Subjects with some components missing at the Week 52 visit will be considered as not achieving sustained remission for the missing components at the Week 52 visit.

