8.1. Primary Efficacy Endpoint

The primary endpoint of this study is the proportion of subjects in sustained remission at Week 52, defined as having achieved all of the following criteria:

1. Remission at Week 12

Remission is defined as having achieved the 2 following criteria:

- a. Clinical remission is defined as absence of clinical signs and symptoms of GCA
And
- b. Normalization of ESR (<30mm/hr) and CRP (<1mg/dL).

A subject in clinical remission is a subject that does not have any signs and symptoms, which is also determined by a lack of flare for the subject. If a subject does have a flare, they will have one or more signs and symptoms, and therefore are not considered as being in clinical remission. A subject without any flare at the Week 12 visit will be considered in clinical remission.

The following rule will be used to assess remission at Week 12:

“Has the patient flared since their last visit?” should be answered “No” at Week 12 visit on the Clinical Assessment of GCA eCRF page and ESR laboratory results value at Week 12 should be < 30mm/hr and CRP laboratory results value at Week 12 should be < 1mg/dL.

AND

2. Absence of disease flare following remission at Week 12 through Week 52

Flare is determined by the investigator and defined as the recurrence of symptoms attributable to active GCA, with or without elevations in ESR and/or CRP.

The following rule will be used to assess absence of disease flare following remission at Week 12 through Week 52:

“Has the patient flared since their last visit?” should be answered “No” at each scheduled and unscheduled visit from any visit after Week 12 up to Week 52 on the Clinical Assessment of GCA eCRF page.

AND

3. Completion of the assigned prednisone taper protocol (to Week 52)

“Can the patient continue with the protocol defined taper” on the Clinical Assessment of GCA eCRF page should be answered “Yes” at all scheduled and unscheduled visits between Baseline and Week 48.

AND

4. No requirement for rescue therapy at any time through Week 52

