8.2.4. Number of Disease Flares per Subject over Time

The cumulative number of disease flares is the total number of flares from first SC IP to the Week 52 visit, as collected in the “Clinical Assessment of GCA” eCRF page. Field “Has the patient flared since their last visit?” will be used to count the number of flares. Scheduled and unscheduled visits will be used.

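### The flare part of the SAP 9.4 signs-and-symptoms table covers scheduled visits only, so symptoms recorded at unscheduled flare visits are left out of it

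*SAP*

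**What the plan says.** - **The table.** SAP 9.4: "A summary table will be provided over time for each scheduled visit, with the number of subjects with each of the signs and symptoms", shown separately for subjects with and without a flare. The same section says the clinical assessment is made every week after Baseline, and that all assessments will be listed.
- **General rule on visits.** SAP 4.4: "Unscheduled visits will not be included in summary tables or figures, with the following exceptions". The exceptions are tables built on all post-baseline assessments (worst, best, maximum, minimum) and tables that report values over a period.
- **What counts as scheduled.** SAP Section 4: "Early withdrawal visits as well as 16-week follow-up visits are considered as scheduled visits". Flare visits are not named.
- **How flare visits are classed.** SAP 9.2.1 describes laboratory sampling at the planned weeks, "including unscheduled visits used to assess flares and early withdrawal visits". SAP 9.2.2 repeats this for serum chemistry.
- **The flare endpoints.** For flare counts, SAP 8.2.4: "Scheduled and unscheduled visits will be used". For the primary endpoint, SAP 8.1 requires that the flare question "should be answered “No” at each scheduled and unscheduled visit from any visit after Week 12 up to Week 52". SAP 8.2.2 applies the same rule up to each Week X.
- **Part B.** SAP Section 11 repeats the Part A safety summaries, and 9.4 sits among them.

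**The concern.** A table of symptoms during flares should draw on the visits at which flares were assessed. By limiting itself to scheduled visits, 9.4 leaves out those the SAP itself describes as held for that purpose. The flare endpoints include them, and no reason is given for the difference.

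The study was terminated early and SAP Section 8 allows only summary statistics for efficacy, so descriptive tables carry what can be said about flares. Section 9.4 is the one post-baseline summary by symptom category (cranial, visual, PMR, other). If part of the flare record is missing, the reported mix of features accompanying flares is incomplete, and with few subjects each omitted record can visibly change a count.

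**Working it through.** The plan states no figure for this point, so there is none to reproduce. The check is a comparison of rules, followed by a day count showing how far apart the scheduled visits are.

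**1. Does an unscheduled flare visit enter the 9.4 table?**
- Section 9.4 names scheduled visits only.
- Section 4 extends that class to early withdrawal and 16-week follow-up visits, and no further.
- Sections 9.2.1 and 9.2.2 class flare-assessment visits as unscheduled.
- Section 4.4 excludes unscheduled visits from summary tables. A table with one row block per scheduled visit is neither an all-post-baseline table nor a table over a period, so neither exception applies.
- Section 9.4 has no rule that moves unscheduled records to another visit.

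The answer is no.

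**2. Worked case.** A subject flares with jaw pain between Weeks 20 and 24, is seen at an unscheduled visit, and is symptom-free at Week 24.
- Section 8.1: the flare after Week 12 fails the no-flare criterion.
- Section 8.2.4: the flare is counted.
- Section 9.4: the jaw pain appears at no visit, either with flare or without.

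**3. Do weekly assessments close the gap?** They would if 9.4 were right about frequency. SAP Table 10 has GCA disease activity at Weeks 2, 4, 8, 12 and then every 4 weeks to 52, which is 14 post-baseline visits.

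**4. Spacing of scheduled visits** (an illustration of the calendar, not a share of flares):
- Part A, ±3 days: 14 windows × 7 days = 98, less 3 days after day 364 = 95. Days outside any window: 1 − 95/364 = 74%.
- Part A after the Week 12 window, days 88 to 364 (277 days): 10 windows × 7 = 70, less 3 = 67. Days outside: 1 − 67/277 = 76%.
- Part B without open-label sirukumab (SAP Table 11), ±5 days: 9 windows × 11 = 99, less 5 after day 728 = 94. Days outside: 1 − 94/728 = 87%.

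There is ample room for flares to be seen between scheduled visits. The documents give no count of flares that were.

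**The case against.** **The ongoing-events rule.** SAP 4.4 also says that events reported on an ongoing basis, "such as cumulative prednisone dose or flare at Week X", are assigned to Week X if they fall after the preceding visit and up to the day of the Week X visit. A table split by flare status at each week could be read under that rule. This is the best counter-argument, and it shows that the authors meant between-visit flares to be counted. But the rule covers flare events. It does not say that symptoms recorded at the unscheduled visit move with them, and 9.4 does not cite it. If only the flare flag moved, Week X symptoms would be paired with an earlier flare.

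**The carry-over rule for remission.** SAP 4.6.2.1 says: "Data recorded at unscheduled visits will be taken into account based on the unscheduled visit date", and ties such data to the next scheduled visit. That is a missing-data rule for sustained remission and does not extend to 9.4.

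**A flare column in the schedule.** Table 10 has one, so a flare visit might be called a protocol visit. Sections 9.2.1 and 9.2.2 still call it unscheduled, and Section 4 omits it where it lists the additions.

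**The content is available elsewhere.** This stands. Clinical assessments are listed (8.1.1, 9.4). SAP 9.1.8 summarizes severe flares as adverse events of special interest, with total or partial blindness, limb claudication, and scalp or tongue necrosis as sub-categories, regardless of visit type. A reader might infer that serious visual loss goes unreported; the documents do not support that.

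**Conclusion.** The point holds as a gap in one descriptive table. Followed as written, 9.4 leaves out symptoms recorded at unscheduled flare visits. Flares present at a scheduled visit are captured, no endpoint or test uses the table, and the primary endpoint is unaffected. It is worth correcting because the fix is cheap and the data are already collected.

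Four stronger readings are tempting and should not be drawn:

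- **That most flares are omitted.** With 28 days between visits, uniform onset and attendance d days after onset, the share seen at an unscheduled visit would be (28 − d)/28: 89%, 75% and 50% for d = 3, 7 and 14. But d is nowhere in the documents, and the formula runs from 100% at d = 0 to 0% at d = 28. The number omitted cannot be computed.
- **That the long late gaps in Part B make it worse.** Completing the gap from Week 52 to Week 76 of Part B takes 52 + 76 = 128 weeks from randomization. Counting back from termination on 10 October 2017 gives 28 April 2015, before the original protocol of 11 May 2015. No subject could have completed that gap by termination.
- **That residual symptoms are misclassified as non-flare at the next visit.** This depends on whether the last visit, in the eCRF flare question, includes an unscheduled one. The documents do not say.
- **That 9.4 and 8.2.4 cannot be reconciled.** One counts subjects with each symptom; the other counts flares and subjects with at least one. The units differ, and the listings connect them.

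**What to change.** In SAP 9.4, keep the rows by scheduled visit and add an any-flare-assessment row or column. It should count subjects with each sign or symptom at any visit, scheduled or unscheduled, where a flare counted under 8.2.4 was recorded. Apply the same addition in Part B. A count over the whole period fits the period exception already in 4.4.

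Do not simply attach the flare visit to the next scheduled visit. Under SAP Section 4, the last non-missing assessment represents a visit with several assessments, so the later record would overwrite the one made during the flare.

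State that 9.4 uses the Safety set by treatment received, whereas 8.2.4 uses the ITT set by randomized arm. Both sets require at least one subcutaneous dose, so overall totals are comparable even if an arm total shifts.

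Replace the weekly assessment statement with the Table 10 visits.

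Cost: SAP wording and a change to one table program. No new data are needed.
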